7.2.3 Exclusion Criteria

Patients meeting any of the following criteria will be excluded from the study:

Medical History

1. Presence of documented secondary sclerosing cholangitis (such as ischemic cholangitis, recurrent pancreatitis, intraductal stone disease, severe bacterial cholangitis, surgical or blunt abdominal trauma, recurrent pyogenic cholangitis, choledocholithiasis, toxic sclerosing cholangitis due to chemical agents, or any other cause of secondary sclerosing cholangitis).
2. Arm 1-3 Only: Biliary intervention within 3 months prior to study enrollment or planned.
3. Arm 4 Only: Planned Biliary intervention between the Screening Period and baseline.
4. Presence of alternative causes of chronic liver disease, including alcohol-associated liver disease, nonalcoholic steatohepatitis, primary biliary cholangitis, autoimmune hepatitis, or active hepatitis B or C.
5. IBD with uncontrolled moderate to severe activity and/or on treatment with any immunosuppressive, immunomodulator, or biologic agent for treatment of IBD (i.e. azathioprine, 6 mercaptopurine, tacrolimus, methotrexate, infliximab, adalimumab, golimumab, vedolizumab, ustekinumab, tofacitinib, ozanimod). Treatment with corticosteroids (including budesonide, budesonide MMX and beclomethasone) in the previous 4 weeks.
6. History of human immunodeficiency virus infection or any other known relevant infection (e.g. tuberculosis).
7. History of ileectomy, colostomy or colectomy.

8. History of malignancy, including hepatocellular carcinoma and cholangiocarcinoma within the past 10 years, except for basal or squamous cell carcinoma of the skin or carcinoma in situ of the cervix that has been successfully treated.
9. Alpha-fetoprotein (AFP) > 20 ng/mL (at the Screening Visit) with 4-phase liver CT or MRI suggesting presence of liver cancer.
10. History of transplants, including liver transplantation, or currently on active transplantation list (Arms 1-3). Arm 4 may be on an active liver transplantation list.
11. Current or a history of hepatic decompensation events including, but not limited to ascites, encephalopathy, or history of esophageal variceal bleeding.
12. Known or suspected overlapping clinical and histologic diagnosis of autoimmune hepatitis.
13. Small duct PSC (evidence of PSC on historical liver histology, with normal bile ducts on cholangiography) without large duct PSC.
14. Liver cirrhosis as assessed by any of the following:
 - a. historical liver histology.
 - b. liver stiffness measurement, assessed by FibroScan (FibroScan value > 14.4 kPa), in addition to clinical assessment and biochemical markers at the discretion of the investigator.
 - c. signs and symptoms of hepatic decompensation (including, but not limited to, jaundice, ascites, variceal haemorrhage, and/or hepatic encephalopathy).
15. History of bacterial cholangitis within 60 days prior to the Screening Period, or if the patient is on antibiotics for prophylaxis of recurrent cholangitis.
16. Females who are pregnant, lactating, or breast feeding as detailed in [Section 9.3.18](#).
17. History of alcohol or substance abuse in the previous 2 years. Patients must agree to refrain from illicit drug (including marijuana) and alcohol use during the study.
18. Hypersensitivity to investigational medicinal product (A3907) and its excipients.
19. Presence of any contraindication for undergoing MRCP (e.g. pacemaker).
20. Any other condition or abnormality which, in the opinion of the investigator (or designee), may compromise the safety of the patient or interfere with the patient participating in, or completing the study.

Treatment Exclusions:

21. Administration of medications that slow gastrointestinal motility ([Section 8.6.2](#)).
22. Treatment with rifampicin.

23. Exposure to oral drugs that are strong inhibitors or inducers of CYP3A4 enzymes (e.g. grapefruit juice, ritonavir, itraconazole, ketoconazole, troleandomycin, rifampin, St John's wort, etc.) within 14 days prior to the Screening Period, or 5 half-lives of the drug, whichever is longer ([Section 8.6.2](#)).
24. Exposure to oral drugs that are substrates of CYP3A4 enzymes (e.g. codeine, ciclosporin [cyclosporin], diazepam, etc.) during the study ([Section 8.6.2](#)).
25. Treatment with vitamin D or fibrates, unless patient is on a stable dose ≥ 6 months prior to baseline.
26. Exposure to an investigational drug, biologic agent, or medical device within 30 days prior to the Screening Period, or 5 half-lives of the study agent, whichever is longer.

Laboratory Exclusions:

27. Platelet count $< 150\,000/\text{mm}^3$.
28. Albumin level $< 3.0\text{ g/dL}$.
29. INR > 1.3 (the patient may be treated with vitamin K intravenously, and if INR is ≤ 1.3 at resampling, the patient may be enrolled).
30. Medical conditions that may cause non-hepatic increases in ALP (e.g. Paget's disease). A GGT or ALP isoenzymes should be obtained for confirmation of biliary origin;
31. Glomerular filtration rate [GFR] $< 60\text{ mL/min/1.73 m}^2$

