5.2.2 PSC with Clinically Relevant Stricture

Strictures are a common radiographic finding in PSC. Dominant strictures are defined as a biliary stricture observed on ERCP with a diameter of ≤ 1.5 mm in the common bile duct or of ≤ 1 mm in the hepatic duct with further delineation in the definition as a high-grade stricture when there is a $> 75\%$ reduction in the common bile duct on magnetic resonance imaging (MRI) ([Bowlus et al., 2023](#)). A clinically relevant stricture is a high-grade biliary stricture on imaging in the common bile duct or hepatic ducts with signs or symptoms of obstructive cholestasis and/or bacterial cholangitis. A clinically relevant stricture is a high-grade biliary stricture on imaging in the common bile duct or hepatic ducts with signs or symptoms of obstructive cholestasis and/or bacterial cholangitis. Forty (40) to 58% of patients with PSC will develop radiographically apparent strictures ([Aljiffry et al., 2011](#)) and

in 15 to 20% of patients with PSC ([Hilscher et al., 2018](#)), a localized CRS is the most prominent feature at diagnosis. Individuals with CRS may be considered a different population in PSC and could be stratified as a cohort separate from those who do not have CRS. The presence of an untreated CRS, even in the absence of bile duct malignancy, has been associated with more advanced liver disease histologically, increased liver stiffness assessment via Fibroscan, facilitation of bacterial colonization, increased risk for cholangiocarcinoma, significantly reduced survival, and, if the stricture is accompanied by high-grade dysplasia, earlier liver transplantation should be considered ([EASL, 2022](#)).

Patients with CRS's are often excluded from PSC clinical trials, especially if a biliary intervention (stent, dilatation) has occurred within the 3 months prior to the Screening Visit. Clinically relevant strictures are typically managed by endoscopic or surgical interventions such as stenting, or dilatation, or resection. These procedures are not without risk and can include recurrent bleeding, infection, bacterial cholangitis, perforation, or pancreatitis. Balloon dilatations of CRS usually need to be repeated at intervals of 1 to 4 weeks; there is no consensus agreement on dilation protocols; and no results are reported in clinical or biochemical improvement after repeat dilations ([EASL, 2022](#); [European Society of Gastrointestinal et al., 2017](#)).

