6.2.3 Exploratory Endpoints

The exploratory endpoints are:

- Change from Baseline to Week 12 in autotaxin
- Change from Baseline to Week 12 in ProC3
- Change from Baseline to Week 12 in high-sensitivity C-reactive protein (hsCRP)
- Change from Baseline to Week 12 in matrix metalloprotease 7(MMP7) and matrix metalloprotease 9 (MMP9)
- Change from Baseline to Week 12 in enhanced liver fibrosis (ELF) and Mayo-PSC score
- Change from Baseline to Week 12 in carbohydrate antigen 19-9 (CA 19-9)
- Change from Baseline to Week 12 in liver stiffness as assessed by FibroScan
- Change from Baseline to Week 12 in pruritus using the daily pruritus scores captured via the Pruritus Numerical Rating Scale (NRS)
- Change from Baseline to Week 12 in fatigue using the daily fatigue scores captured via the fatigue NRS
- Change from Baseline to Week 12 in sleep disturbance using the daily sleep disturbance scores captured via the sleep disturbance NRS
- Change from Baseline to Week 12 in mood using the daily mood scores captured via the mood Likert scale
- Episodes of cholangitis requiring antibiotic use in the 12 weeks prior to dosing versus the 12 weeks after dosing

Additional Exploratory Endpoints, Arm 4 Only

- Change of model for end-stage liver disease (MELD) score from baseline to Week 12
- Change in endoscopic biliary dilation intervals/ frequency in the 12 weeks prior to study start (V2) compared to the 12-week treatment period for those subjects who are regularly dilated.

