7.2 Study Population

7.2.1 Number of Patients

Approximately 24 patients are expected to be treated in this study. Six patients are planned to enroll in each of the 4 treatment arms of the study.

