9.2. Clinical Laboratory Evaluations

Clinical safety laboratory evaluations will be performed by a central laboratory. Samples will be collected for clinical laboratory evaluations at timepoints indicated in [Table 1](#) and [Table 2](#). Safety lab parameter like clinical chemistry and urinalysis ([Appendix 2](#)) will be presented from Baseline up to Follow-Up after 12-Week Treatment. Hematology will be presented at Baseline, Start of 12-Week Treatment up to Follow-Up after 12-Week Treatment. Coagulation will be presented at Baseline, Start of 12-Week Treatment, Week 4 of 12-Week Treatment and Week 12 of 12-Week Treatment.

Descriptive statistics for clinical laboratory values [chemistry, hematology, urinalysis, coagulation laboratory tests, LBTs including aminotransferase (ALT and AST), GGT, ALP, and total and direct bilirubin levels] will be presented. For LBTs, 2-sided 95% CI of the mean for relative and absolute change from baseline 1 to each post-baseline visit and the last visit, and actual values at each visit will be presented along with descriptive statistics. Relative and absolute changes from baseline 1 to each post-baseline visit and the last visit will also be presented for quantitative variables. For clinical chemistry assessments and urinalysis tests with quantitative results, baseline 1 is defined as the average of all Screening results and results on the day of the planned single dose if both results are available. Otherwise, baseline 1 will be defined as the last non-missing assessment prior to the study drug administration of planned single dose. For other laboratory parameters, baseline 1 is defined as the last non-missing assessment of that parameter prior to the study drug administration of planned single dose. For categorical variables (i.e., normal or abnormal findings, or qualitative clinical laboratory tests), a table of categorical values over time will be presented. Results of quantitative clinical laboratory values will be categorized as low, normal, or high according to laboratory range specifications. Shifts from baseline 1 to each scheduled post-baseline time point will be presented to show the number and percentage of patients in each category by parameter.

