9.7. MELD Score

For Arm 4, the MELD score will be calculated as follows:

$$\text{MELD Score} = 9.57 \times \ln(\text{creatinine mg/dL}) + 3.78 \times \ln(\text{total bilirubin mg/dL}) + 11.2 \times \ln(\text{INR}) + 6.43$$

The MELD Na Score will be calculated as follows:

$$\text{MELD Na Score} = \text{MELD} - \text{Na (mEq/L)} - [0.025 \times \text{MELD} \times (140 - \text{Na (mEq/L)})] + 140$$

For calculation of the MELD score, laboratory values less than 1.0 will be set to 1.0 and serum creatinine values greater than 4.0 mg/dL (equivalent to 353.6 $\mu\text{mol/L}$) will be set to 4.0. For calculation of the MELD Na score, sodium (Na) values greater than 140 mEq/L will be set to 140 and values less than 125 mEq/L will be set to 125.

For Arm 4, absolute change from baseline 1 in MELD score will be presented for the Safety Analysis Set. Similar summary tables presenting absolute change from baseline 2 for the 12-week treatment period will be presented for MELD scores for patients in the Safety Analysis Set who actively entered 12-Week treatment period. Supporting listing will also be presented for the Safety Analysis Set.

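### Arm 4 changes in bile acids, liver tests and MELD cannot be separated from the effect of biliary interventions during treatment, and the bias could go either way

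*Protocol*

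**What the plan says.** Protocol 7.2.3 treats the arms differently. Exclusion 2 removes a patient for "Arm 1-3 Only: Biliary intervention within 3 months prior to study enrollment or planned". Exclusion 3, the only counterpart for stricture patients, reads "Arm 4 Only: Planned Biliary intervention between the Screening Period and baseline". It covers planned procedures only and ends at baseline. Section 8.6 restricts medications and does not mention biliary procedures.

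Procedures on treatment are foreseen. Protocol 5.2.2 says "Balloon dilatations of CRS usually need to be repeated at intervals of 1 to 4 weeks", which over 12 weeks would be 3 to 12 dilations if kept up. Protocol 6.2.3 makes dilation intervals and frequency before Visit 2 an Arm 4 endpoint, "compared to the 12-week treatment period for those subjects who are regularly dilated". The schedule of assessments documents dilation data at Visits 1, 2 and 7.

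On the analysis side:
- For clinical chemistry, SAP 9.2 says "baseline 1 is defined as the average of all Screening results and results on the day of the planned single dose", if both are available. SAP 8.2.1 does the same for serum bile acids.
- Changes are then given at each post-baseline visit, with 95% CIs of the mean for bile acids and liver tests.
- SAP 9.7 says "For Arm 4, absolute change from baseline 1 in MELD score will be presented for the Safety Analysis Set".
- The same variables are also reported against baseline 2, the last value before the 12-week period.
- SAP 9.8 summarises dilation in a table of its own.

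**The concern.** Liver tests, bile acids and the bilirubin term of MELD are cholestasis markers that could plausibly move after a stricture is dilated or stented. If so, an Arm 4 value depends on both the drug and the time since the last procedure, and the plan reports only the combined result.

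Nothing in the design separates the two. The study is open label without a reference therapy, and Protocol 7.2.1 states "Six patients are planned to enroll in each of the 4 treatment arms of the study". Liver tests and bile acids are secondary endpoints and MELD is exploratory. Arms 3 and 4 are the only two arms on the same planned dose, so a reader will set them side by side, although procedures are screened out in one and expected in the other.

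**Working it through.** The plan has no power calculation, effect size or SD, so there is no figure of its own to reproduce.

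**Inputs from the documents.** Arm 4 has n = 6. CIs are two-sided 95%. The MELD bilirubin coefficient is 3.78, with laboratory values below 1.0 set to 1.0 (Protocol 9.3.10, SAP 9.7). Visits 1, 2, 3, 4 and 7 fall on protocol Days -14, 0, 14, 28 and 98.

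**Assumptions, not in the documents.** The drug is inactive. Of the 6 patients, k have a percentage fall f because of an intervention. The SD of percentage change is 15 to 30 points, and f is 20% to 50%.

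**Step 1: shift in the Arm 4 mean.** Shift = -f × k/6. With f = 30%:
- k = 1: -30 × 1/6 = -5%
- k = 3: -30 × 3/6 = -15%
- k = 6: -30%

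**Step 2: chance that the t-based 95% CI lies wholly below zero** (simulation, normal errors):

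| k | f = 30%, SD 20 | range over f 20–50%, SD 15–30 |
|---|---|---|
| 0 | 2.5% | 2.5% |
| 1 | 4.4% | 2.3% to 4.4% |
| 3 | 16.5% | 8% to 22% |
| 6 | 83.2% | 26% to 100% |

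One dilated patient barely changes the CI behaviour, because the outlying value also widens the interval. The problem grows when half or more of the arm is affected.

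**Step 3: MELD.** Change = 3.78 × ln(bilirubin after / before). If bilirubin halves from 2 mg/dL or more, the change is 3.78 × ln 0.5 = -2.62 points in that patient. The Arm 4 mean then moves by -0.44, -1.31 or -2.62 for k = 1, 3 or 6. A 25% fall that stays above the floor gives 3.78 × ln 0.75 = -1.09. A start at or below 1 mg/dL gives 0. Inclusion 6 caps bilirubin only in Arms 1-3. However, Inclusion 14 admits increasing jaundice in Arm 4 while Exclusion 14c lists jaundice as a sign of decompensation. Those passages must be reconciled, because they decide how far bilirubin can fall.

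**Step 4: direction.** Steps 1 to 3 assume a fall. To see whether timing fixes the sign, take a strict 28-day dilation cycle with a marker rising as r^(days since dilation/28). Visit 1 is p days after a dilation (p from 0 to 14), so none is due before Visit 2. Baseline 1 is r^(p/28) × (1 + √r)/2.
- Visit 4 is 42 days after Visit 1, so it is p + 14 days into the cycle. The ratio to baseline 1 is √r / ((1 + √r)/2). For r = 1.3 this is 1.140/1.070, or +6.5%. For r = 2 it is 1.414/1.207, or +17%.
- Visit 7 is 112 = 4 × 28 days after Visit 1, so it is at p again. The ratio is 1 / ((1 + √r)/2), giving -6.5% or -17%.

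The same patient with an inactive drug looks worse at Visit 4 and better at Visit 7.

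**Step 5: baseline 2.** In this example the next dilation falls between Day 0 and Day 14, where nothing restricts it, and Visit 3 is also at p. Against baseline 2, Visit 7 shows no change, but Visit 4 shows √r - 1, which is +14% or +41%. Baseline 2 therefore does not remove the problem.

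**The case against.** **No documented effect.** Protocol 5.2.2 says "no results are reported in clinical or biochemical improvement after repeat dilations", so the sponsor can argue that there is nothing to adjust for. This stands in part: the size of any procedure effect is an assumption, and it could be small. But an absence of reported results is not evidence of no effect.

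**Limited stakes.** The primary endpoint is TEAEs. The affected analyses are descriptive, no test of Arm 3 against Arm 4 is planned, and those arms already differ in bilirubin limits and transplant listing. Possibly none of the six patients is regularly dilated. Separate listings of dilation, laboratory and MELD data are planned. All of this is correct, and it is why the point calls for a cheap improvement rather than a redesign.

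**A stronger reading that a reader might infer.** Because Exclusion 3 keeps planned dilations out of the screening window, one might conclude that baseline always sits late in the dilation cycle and that the bias must favour A3907. Suppose Visit 1 falls at random in the cycle, a due dilation is postponed past Visit 2, and on-treatment values fall at random in the cycle. The geometric mean change from baseline 1 is then 1/((1 + √r)/2) - 1 for a 28-day cycle, or -6.5% to -17% for r = 1.3 to 2. For a 14-day cycle it is 2/(1 + r) - 1, or -13% to -33%.

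The documents do not support that model:
- Exclusion 3 removes patients with a dilation planned in the window, and no document describes postponing one.
- With only on-schedule, eligible patients, the figures become r^0.25 / ((1 + √r)/2) - 1, or -0.2% to -1.5% (28 days), and √r / ((1 + r)/2) - 1, or -0.9% to -5.7% (14 days).
- Step 4 shows that the sign can reverse between visits. A dilation shortly before Screening, which Arm 4 has no washout to prevent, would lower baseline and work against the drug.
- The screening check on ALP variability (Inclusion 5) would question some of the steeper assumed rises, although a third in-range value still allows entry.

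**Conclusion.** The point holds as a problem of attribution, not as a bias of known sign. Interventions in Arm 4 are unrestricted after baseline and expected in regularly dilated patients, yet they play no part in the analysis of bile acids, liver tests or MELD. With six patients and no control arm, an Arm 4 change in these variables cannot be ascribed to A3907 rather than to a procedure.

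The size cannot be taken from the documents. The illustrative shifts in Step 1 and CI probabilities in Step 2 depend on the assumed fall, the SD and the number dilated. They show that the effect is minor with one dilated patient and could dominate the result with six. The primary safety analysis is outside this point. The change is worth making because it is cheap and improves what Arm 4 can show.

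**What to change.** In SAP 8.2, 9.2 and 9.7, for Arm 4 only:

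1. Flag each value obtained after a biliary intervention (dilation or stent) since Day 0. List days since the last intervention beside baseline 1, baseline 2 and every visit value. This exposes bias in either direction.
2. Show change from baseline for all Arm 4 patients, and separately for patients with and without any intervention from Day 0 to Week 12.
3. State that an Arm 4 change present only in patients with an intervention cannot be distinguished from a procedure effect.

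A table restricted to values before the first intervention is not a useful substitute. In patients dilated every 1 to 4 weeks it would hold almost no on-treatment values.

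The cost is SAP wording, a listing column and one extra table. Dilation data are already documented at Visits 1, 2 and 7, and non-drug therapies are recorded throughout (Protocol 8.6). The sponsor should confirm that intervention dates are captured. The subgroups will be very small, and one will be empty if all or none of the six patients are dilated. They are also defined by events after baseline, so the split is descriptive and not an estimate of drug effect. No clinical rule is changed.

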7.2.4 Withdrawal of Patients

7.2.4.1 Individual Study Drug Interruption and/or Discontinuation

Study drug administration will be discontinued for patients with C_{max} or AUC that exceed the safety margins observed in the FIH study ([Section 5.4](#)), or because of circumstances leading to study withdrawal as detailed in [Section 7.2.4.2](#).

A patient will discontinue dosing but may remain in the study for safety monitoring if any of the following criteria are met:

- A patient's desire to discontinue study drug for any reason.
- Any AE considered related to A3907 that in the opinion of the investigator (or designee) and sponsor's medical monitor poses a risk to the patient's safety or well-being and warrants study drug discontinuation ([Section 9.3.6](#)).
- Liver transplantation.
- Pregnancy

- A patient's exposures exceed the arm's highest systemic exposures previously achieved in healthy subject CCI

CCI

The reason and date the patient is discontinued from the treatment will be documented in the electronic case report form (eCRF). The patient will undergo End-of-Treatment and End-of-Study procedures as defined in [Table 1](#).

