
Methodology:
 
This is an open-label, Phase 2 study to evaluate the safety, tolerability, PK, and pharmacodynamic (PD) effects of 3 dose levels of A3907 (10 mg once daily [QD], 30 mg QD and 30mg twice daily [BID] administered orally for 12 weeks) in patients with PSC with and without a CRS.
 
The study includes up to a 2-week Screening Period, followed by administration of a single dose of A3907, followed by a 2-week period to confirm target exposure is reached before beginning a treatment period of 12 weeks, and an End of Study Visit 14 days after the last dose of study drug.
 
There will be a total of 8 scheduled visits during the study (including 1 Screening Visit).
 
The study will have four arms as follows:
 
 • Arm 1: patients with PSC dosed with 10mg QD • Arm 2: patients with PSC dosed with 30mg QD • Arm 3: patients with PSC dosed with 30mg BID • Arm 4: patients with PSC who have a CRS dosed with 30mg BID 
On Day 0, patients will receive a single daily dose of A3907 (10 mg QD [Arm 1], 30 mg QD [Arm 2], 30 mg BID [Arms 3 and 4]). Before each patient can begin the 12-week Treatment Period, individual PK evaluations will be conducted to ensure study drug exposure does not exceed the safety margin described in Section 5.4. If the exposures (C_{max} and AUC) exceed the highest systemic exposure as determined by the single ascending dose (SAD) data from the first in human (FIH) study, the individual patient will be terminated early.
 
Staggered Arms
 
Enrollment into treatment arms will be staggered as follows:
 
 • Arm 2 will begin after at least 3 patients in Arm 1 have completed 2 weeks of treatment and an internal Safety Review Committee (SRC) has reviewed safety and PK data; • Arms 3 and 4 will begin after at least 3 patients in Arm 2 have completed 2 weeks of treatment and the SRC has reviewed safety and PK data. Enrollment into Arm 4 will occur concurrently with Arm 3. 
Safety Review Committee (SRC)
		

Name of Sponsor/Company: Albireo AB	Name of Product: A3907	Name of Active Ingredient: A3907

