In a first-in-human (FIH) study (Study A3907-001), A3907 or matching placebo were administered in capsules to healthy subjects as single oral doses of C to C mg or CCI oral doses of CCI mg for 7 days. Overall, A3907 was well tolerated when administered as single and multiple ascending doses (SAD/MAD) to the healthy subjects. There were no serious adverse events (SAEs), all treatment-emergent adverse events (TEAEs) were mild in

severity, and no subjects discontinued study drug or withdrew from the study due to TEAEs. The only treatment-related AEs that occurred in ≥ 2 subjects following single or multiple doses of A3907 were diarrhoea, abdominal pain, and headache. Pharmacokinetic analysis revealed that, with this formulation, A3907 was slowly absorbed (T_{\max} approximately [REDACTED] hours) and dose proportionality was demonstrated at single doses of [REDACTED]; the higher single dose of [REDACTED] mg did not result in increased exposure. No accumulation was seen following multiple [REDACTED] doses of [REDACTED] mg for 7 days, consistent with a half-life of approximately [REDACTED] hours. An increase in serum C4 concentrations and a decrease in serum LDL-C concentrations was observed at all A3907 doses; exploratory PK/pharmacodynamics (PD) results suggested a weak correlation between these PD parameters and A3907 PK parameters. While no clear trends were seen between A3907 concentrations and serum total bile acid concentrations, there was a decrease in total urine bile acids excreted at all treatment doses compared to placebo. Together, results of this study suggest that A3907 does inhibit ASBT but the net effect in the intended population is yet to be determined.

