This is the first time A3907 will be administered to patients with PSC. Potential risks in the patient population are unknown. The potential risks associated with A3907 treatment will be mitigated by routine monitoring as noted in [Section 9.3](#). The study has been designed with a lead-in period to determine the exposure of A3907 in individual patients to ensure that exposure levels observed at the highest dose level in A3907-001 are not exceeded. Additionally, enrollment into Arm 2 will only begin after at least 3 patients in Arm 1 have completed 2 weeks of treatment at the lower dose and an SRC has reviewed safety and PK data ([Section 10.2.5](#)). For Arms 3 and 4, enrollment will only begin after at least 3 patients in Arm 2 have completed 2 weeks of treatment at the 30 mg dose QD dose, and an SRC has reviewed safety and PK data ([Section 10.2.5](#)). The SRC will also review safety data from this study on an ongoing basis and after the last patient reaches 12 weeks. Thus, exposure of patients in this study is justified by the anticipated benefits that may be afforded to the wider population of patients by continued development of A3907.

Benefit assessment

This study is designed to evaluate the safety, tolerability, PK, and PD of A3907 in patients with PSC. The dose selected is expected to reduce bile acid transport, leading to a decrease in serum bile acids, and positively influence liver enzymes and markers of liver fibrosis. It is not known whether patients participating in this study will benefit from the treatment. Due to the short duration of this study, any benefit observed is not expected to persist beyond the end of the study. However, the increased understanding of the effects of A3907 in this population may potentially result in new treatment options that would ultimately benefit patients with PSC.

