3.3.1. Treatments Administered

The study includes up to a 2-week Screening Period, followed by administration of a single dose of A3907, followed by a 2-week period to confirm target exposure is reached before beginning a treatment period of 12 weeks. Each patient's PK will be reviewed and, if the systemic exposures do not exceed the highest systemic exposure previously established in the SAD portion of the FIH study (C_{max} of CCI ng/mL or AUC of CCI ng h/mL), the dose will be confirmed and the patient will begin administration of A3907 daily for 12 weeks. If the exposures exceed the highest systemic exposure, the individual patient will be terminated early.

Study drug will be dispensed to the patient at defined intervals from Visit 3 through Visit 7, together with instructions on how to store and take the drug. Study drug administration data, including whether each patient took each dose, will be documented through the Patient Diary and transferred to the study database at each visit.

4. General Statistical Considerations

In general, descriptive statistics will be presented by treatment arm and by visit, as applicable. Continuous data will be summarised using descriptive statistics (i.e., n, mean, standard deviation (SD), or standard error (SE), median, minimum, and maximum). Categorical data will be summarised using the patient count and percentage in each category. Non-zero percentages will be rounded to one decimal place, except 100% will be displayed without any decimal places. For the summary statistics of all numerical variables unless otherwise specified, minimum and maximum will be displayed to the same level of precision as reported up to a maximum of three decimal places. Mean and median will be displayed to one level of precision greater than the data collected up to a maximum of three decimal places. Standard deviation and standard error will be displayed to two levels of precision greater than the data collected up to a maximum of four decimal places. When count data are presented, the percentage will be suppressed when the count is zero to draw attention to the non-zero counts. Unless otherwise specified, all confidence intervals (CI) will be 2-sided and performed using a 5% significance level. Confidence intervals will be

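### The individual exposure check after the single dose joins Cmax and AUC by *and* in the synopsis but by *or* in Protocol 7.2.4.1 and SAP 3.3.1, and its reference level and consequence are also worded inconsistently

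*Protocol*

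**What the plan says.** **Connector.**
- Protocol synopsis (Methodology): "If the exposures (C_{max} and AUC) exceed the highest systemic exposure as determined by the single ascending dose (SAD) data" from the first-in-human (FIH) study, the patient's participation ends.
- Protocol 7.2.4.1: drug is stopped for a Cmax "or AUC that exceed the safety margins observed in the FIH study", with a pointer to Section 5.4.
- SAP 3.3.1: the dose is confirmed if exposures do not exceed the single ascending dose (SAD) maximum, given as "C_{max} of CCI ng/mL or AUC of CCI ng h/mL".
- Protocol 5.4, 7.1.1 and 8.2 speak only of exposures. Their visible text has no connector.

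**Reference level.**
- The synopsis, 5.4, 7.1.1 and SAP 3.3.1 use the highest exposure in the SAD part of A3907-001.
- A bullet in 7.2.4.1 applies when a patient's "exposures exceed the arm's highest systemic exposures previously achieved in healthy subject". The rest of that bullet is redacted.
- Section 5.5 describes the lead-in as a means "to ensure that exposure levels observed at the highest dose level in A3907-001 are not exceeded".
- Section 8.2 refers to exposure seen in the FIH study, then points to 5.4.

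**Consequence.**
- SAP 3.3.1: "If the exposures exceed the highest systemic exposure, the individual patient will be terminated early". The synopsis, 5.4, 7.1.1 and 8.2 say the same in substance.
- 7.2.4.1 lists the exposure criterion among those for which dosing stops but the patient can stay on study for safety follow-up, with End-of-Treatment and End-of-Study procedures.
- Table 1 footnote b calls for an End-of-Study Visit when a patient is ended after Visit 2 for high exposure.

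**The concern.** Section 5.5 says that this is the first use of A3907 in PSC and that the risks in this population are unknown. It names the single-dose lead-in as a mitigation. Section 5.4 expects individual PK to vary with food, gut transit and liver impairment, and the drug is now a tablet rather than the capsule used in the FIH study. A profile that is high on one metric but not the other is therefore plausible.

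For such a patient, the section that a site or medical monitor happens to read decides whether 12 weeks of dosing begins. It also affects who contributes repeat-dose safety, PK and PD data in arms of 6. Replacement is affected too: Protocol 7.1.1 allows it for patients withdrawn or ended early, and a patient who is off drug but still on study is not clearly either.

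**Working it through.** The documents give no figure to reproduce: the Cmax and AUC limits are redacted and no exceedance rate is stated. The check is therefore logical, followed by an illustration on assumed inputs.

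**Step 1: decisions under each connector.** Take one fixed pair of limits and read each wording literally.

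| Cmax above limit | AUC above limit | *and* (synopsis) | *or* (7.2.4.1, SAP 3.3.1) |
|---|---|---|---|
| no | no | continue | continue |
| yes | no | continue | stop |
| no | yes | continue | stop |
| yes | yes | stop | stop |

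The wordings disagree in 2 of the 4 states, those where exactly one metric is exceeded.

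**Step 2: illustrative size (assumed inputs).** Let each metric exceed its limit with probability *p*, and let log Cmax and log AUC be bivariate normal with correlation *r*. Then:
- P(both) is the joint upper tail beyond z(1−*p*) on each axis
- discordant fraction *d* = 2 × (*p* − P(both))
- expected number = 24 × *d*, where 24 is 4 arms × 6 patients (Protocol 7.2.1)
- chance of at least one = 1 − (1 − *d*)^24

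| *p* | *r* | P(both) | *d* | Expected of 24 | P(at least one) |
|---|---|---|---|---|---|
| 0.02 | 0.50 | 0.0034 | 0.0332 | 0.80 | 0.556 |
| 0.02 | 0.95 | 0.0140 | 0.0121 | 0.29 | 0.252 |
| 0.05 | 0.50 | 0.0122 | 0.0756 | 1.81 | 0.849 |
| 0.05 | 0.95 | 0.0371 | 0.0258 | 0.62 | 0.466 |
| 0.10 | 0.50 | 0.0324 | 0.1352 | 3.24 | 0.969 |
| 0.10 | 0.95 | 0.0779 | 0.0442 | 1.06 | 0.662 |
| 0.20 | 0.50 | 0.0872 | 0.2257 | 5.42 | 0.998 |
| 0.20 | 0.95 | 0.1646 | 0.0707 | 1.70 | 0.828 |

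Worked line, *p* = 0.10 and *r* = 0.50: *d* = 2 × (0.10 − 0.0324) = 0.1352, and 24 × 0.1352 = 3.24. Values of *d* come from unrounded P(both), so the last digit can differ from a hand calculation. The calculation uses one *p* for all arms, although the dose ranges from 10 mg QD to 30 mg BID.

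**Step 3: reference level.** Four statements agree on the SAD maximum. Two use other words: the highest for the arm (7.2.4.1) and the level at the highest dose (5.5). Section 5.2.3 reports that the higher single dose of "mg did not result in increased exposure", so the highest dose and the highest exposure need not coincide. With the values redacted, no difference can be calculated.

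**Step 4: consequence.** Ending participation early and stopping drug while staying on study can be the same event only if the first means ending treatment. No section says so.

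**The case against.** The synopsis *and* sits in a parenthesis after the word exposures and may only list the two metrics checked. The sentence before it refers to the safety margin in 5.4, as does 7.2.4.1. The section that governs discontinuation says *or*, and so does the SAP. Where SAP 3.3.1 prints its limits, 5.4 and 7.1.1 show a redaction, so the same *or* may lie beneath it. All of this is fair, and it makes the conflict an ambiguity rather than proof of two intended rules. It does not remove the conflict: the connectors in the synopsis, 7.2.4.1 and SAP 3.3.1 are visible and differ, and a safety check should not depend on how a parenthesis is read.

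Other parts of the objection stand in full:
- A reader might infer that the reference levels are different numbers. The documents do not show this. The values are redacted, 7.2.4.1 and 8.2 point back to 5.4, Section 5.5 is risk/benefit narrative, and the finding in 5.2.3 also fits a plateau where the levels are close.
- A reader might infer that the 7.2.4.1 bullet leaves the rule open in time. Its end is redacted, and the synopsis, 5.4, 7.1.1 and 8.2 place the check before the 12-week period.
- A reader might infer that the visit requirements clash. Footnote b covers this very case, and 7.2.4.1 defers to Table 1.
- A reader might infer that stopped patients leave the primary analysis. They do not: the safety set holds everyone with at least one dose.

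**Conclusion.** The point holds as an inconsistency in the wording of an individual safety check. The connector conflict is in visible text and gives opposite decisions, on a literal reading, for a patient above exactly one limit. When both or neither metric is exceeded, the two wordings agree. The reference and the consequence are also worded inconsistently, but only as wording: no numerical gap between references is shown.

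The number of patients affected is unknown. Under assumed exceedance of 2% to 20% per metric and correlation 0.5 to 0.95, it is about 0.3 to 5.4 of 24, with a 25% to 99.8% chance that at least one is affected. Those inputs are not in the documents, and the range shows scale only. The conflict in wording does not depend on them.

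**What to change.** Reconcile the synopsis, Protocol 5.4, 5.5, 7.1.1, 7.2.4.1 and 8.2, Table 1 footnote b and SAP 3.3.1 to one identical statement that gives:
1. the connector between Cmax and AUC;
2. the single FIH reference level;
3. the consequence (off drug only or off study), with the visits that follow and whether the patient may be replaced.

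The sponsor decides which version applies. This review does not choose between them.

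Also list each patient's Day 0 Cmax and AUC (Day 1 in the SAP) as ratios to the chosen reference, with the decision taken. SAP 8.1 sends PK results outside the Clinical Study Report, so the SAP should say where this listing will appear. If the checks have already been made, record which wording was applied to each patient.

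The cost is aligned wording in one protocol amendment, one SAP sentence and one short listing. No new samples or visits are needed.
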